### *Close out:*

- *Thank you again for your time today.* We will talk to you on [date/time] to complete your telephone interview and on [date/time] to complete your 2nd in person study visit.
- *For your in person study visit,* We ask that you do not to not drink any caffeine (from coffee, tea, or soda), should not eat or do any heavy physical activity, smoke, ingest alcohol for 30 minutes prior to the in person data collection visit. *Please wear a loose fitting shirt to the study visit.*
- Thank you and have a wonderful day!

## Living Well Program Participant Phone Call Script – Month 2

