**Notes**

F1. We are now finished with the interview. Thank you so much for taking time today to answer these questions. The next step is to schedule an in-person data collection. As we mentioned before, during this visit, Living Well Program research assistants will measure your blood pressure, blood sugar, cholesterol, weight, and height.

- Wearing a loose fitting shirt is recommended to the in-person data collection visit so that we are able to measure your blood pressure.
- We ask that you not to drink any caffeine (from coffee, tea, or soda), eat, do any heavy physical activity, smoke, or ingest alcohol for 30 minutes prior to the in person data collection visit.

There are 2 options for this visit, which will last from 45-60 minutes. Option 1 is Living Well research assistants to come to your home to do the measurements. Option 2 is for you to meet us a data collection visit that is scheduled at a community venue in your community.

Are you interested in the in-home data collection or would you like to meet us for a group data collection day?

In home data collection preferred: (schedule date / time / location & directions)

Group data collection at community venue preferred: (schedule for a data collection)

The next data collections in your area are scheduled for \_\_\_\_\_(DATE / TIME) at \_\_\_\_\_(LOCATION).

Which dates/times are convenient for you? [Schedule data collection] \_\_\_\_\_

F2. [Scheduled data collection] Great! I have your data collection date scheduled for [date / time / location].

You will receive a reminder card in the mail at this address 5 -7 days before this date. You will also receive a telephone call to remind you of the date the day before the visit.

F3. Verify telephone / contact information:

F4. Verify location / directions:

F5 Great! I have your data collection date scheduled for [date / time / location]. A research study assistant will meet you at (\_\_\_\_\_ location) and at (\_\_\_\_\_ time/date).

Thank you so much! Have a great day.

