### 3. Measurement Procedures.

The blood pressure can be measured after any period where the participant has been sitting quietly (no talking or completing forms) for 5 or more minutes, and at least 30 minutes after ingestion of caffeine. After applying the appropriate sized blood pressure cuff, the participant should sit for 5 minutes with his/her feet flat on the floor and legs and ankles uncrossed. Two blood pressure readings will be obtained.

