### **I am calling today to check in with you and remind you that your 2nd study visit and telephone interview are coming up in 1 month.**

- Have you spoken to your peer advisor? How many times in the past 4 weeks have you spoken to your peer (NAME HERE)
- Your 2nd telephone interview and your study visit are coming up in 1 month. Let me tell you a little about these visits. During the telephone interview, we will ask you some questions about you and your diabetes. At the in-person data collection visit, UAB staff will do a finger stick test to check your A1c number, which is your average blood sugar level, and your blood cholesterol. They will also measure your height, weight, blood pressure, and make a list of your medications.
- Remember, you will receive a \$20 VISA gift card for completing the inperson study visit.
- Would you like to schedule this visit and telephone interview today?
  - o if no: Okay, I will give you a in 2-3 weeks.
  - o If yes, schedule date and times: Great! We will call you on the phone and send you a reminder in your mail before the visits as a reminder.
- May I answer any questions that you may have about the study?

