### **I would like to verify your contact information. Is this your correct mailing address and telephone number?**

**Yes – great thank you!** *(move to next question)*

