### ***Close out:***

- ***Thank you again for your time today.*** We will talk to you on [date/time] to complete your telephone interview and on [date/time] to complete your 2nd in person study visit. Thank you and have a wonderful day!

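### The month-5 scripts give the pre-visit blood pressure preparation to the General Health arm only, and no form item checks it, so unequal preparation by arm at the 6-month visit would go unseen

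*Combined protocol and SAP*

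**What the plan says.** **General Health arm, month 5 (Appendix G, Retention Scripts, Close out).** The caller gives the interview and visit dates, then the preparation: "We ask that you do not to not drink any caffeine (from coffee, tea, or soda"). Food, heavy physical activity, smoking and alcohol are added, all for the 30 minutes before the visit. The caller also says: "Please wear a loose fitting shirt to the study visit".

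**Living Well arm, month 5.** The description of the coming visit is nearly identical. The close-out gives only the dates ("We will talk to you on [date/time] to complete your telephone interview and on [date/time") and thanks the participant. The script contains neither the abstention nor the clothing request. For participants who schedule on the call it does promise later contact: "We will call you on the phone and send you a reminder in your mail before the visits as a reminder".

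**Baseline, all participants.** The eligibility script (Appendix D) and item F1 closing the baseline telephone interview (Appendix E) both give the abstention: "We ask that you not to drink any caffeine (from coffee, tea, or soda"), and so on. Item F1 also recommends a loose shirt.

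**Measurement rule, all participants (Appendix F, Blood Pressure).** Section 2 requires the 30-minute abstention before the reading, without reference to arm. Section 3 allows the reading after five quiet seated minutes and "at least 30 minutes after ingestion of caffeine".

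**At the visit.** Step 1 of the In-person Data Collection Form covers batteries, cuff, posture, a quiet room and the rest period. Neither it nor the blood pressure quality assurance checklist (4.3) has an item on the preceding 30 minutes.

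**The concern.** Blood pressure is one of the outcomes listed in the Appendix F introduction. The preparation instruction is part of how that outcome is measured, and in the month-5 scripts it differs by randomised arm. Nothing suggests that this was intended; it reads like a paragraph missing from one of two parallel scripts.

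If more Living Well participants arrive having just had caffeine, smoked, eaten or exerted themselves, and staff do not catch it, their readings shift for a reason unrelated to the program. A larger sample does not remove such a shift. If unprepared readings run high, the shift works against the program and could mask a true benefit. Because the form has no field for preparation, an imbalance could be neither seen nor adjusted for at analysis.

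**Working it through.** The plan states no figure on this point, so there is none to reproduce. The check compares the texts and then shows what an imbalance would do.

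**Step 1. Compare the contacts and controls.**

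| Place | General Health | Living Well |
|---|---|---|
| Eligibility script and baseline interview | abstention given | abstention given |
| Month-5 script: 30-minute abstention | given | absent |
| Month-5 script: loose shirt | given | absent |
| Month-5 script: promise of phone and mail reminders | absent | given; reminder text on preparation not shown |
| Follow-up interview script | not shown | not shown |
| Biometric protocol, Blood Pressure sections 2 and 3 | same rule | same rule |
| Form Step 1 and checklist 4.3: item on the last 30 minutes | none | none |

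The difference by arm lies in the month-5 instruction. The required preparation is the same in both arms. No shown form or checklist item verifies it. The 6-month reminder cards that are shown do not mention it either.

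**Step 2. Formula for the bias.** Let q be the share measured unprepared in Living Well minus the share measured unprepared in General Health, and d the average systolic shift in an unprepared reading.

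Bias = q × d

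The relevant share is the difference between arms. Using the Living Well share alone would assume that every control arrives prepared.

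**Step 3. Inputs.** From the documents: 250 participants per arm. Assumed, because the documents give no value: q of 10% to 30%, d of 2 to 10 mmHg, and a systolic standard deviation (SD) of 15 to 20 mmHg. All 250 per arm are taken as measured, without baseline adjustment.

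SE = SD × √(2/250): 15 × 0.0894 = 1.34 mmHg, and 20 × 0.0894 = 1.79 mmHg.

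**Step 4. Results.** The last column is the chance that a two-sided 5% normal test rejects when the program has no true effect.

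| q | d (mmHg) | Bias (mmHg) | Bias / SE (SD 20 to SD 15) | Rejection rate (SD 20 to SD 15) |
|---|---|---|---|---|
| 0 | any | 0 | 0 | 5.0% |
| 10% | 2 | 0.2 | 0.11 to 0.15 | 5.1% to 5.3% |
| 10% | 5 | 0.5 | 0.28 to 0.37 | 5.9% to 6.6% |
| 10% | 10 | 1.0 | 0.56 to 0.75 | 8.6% to 11.6% |
| 30% | 5 | 1.5 | 0.84 to 1.12 | 13.4% to 20.1% |

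More extreme pairs give more: 50% and 10 mmHg would give 5.0 mmHg. Nothing in the documents points to values that large. If staff apply sections 2 and 3 at every visit, q is near 0 and so is the bias.

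**The case against.** The strongest reply is that the measurement rule, not the script, decides how blood pressure is taken, and that rule is common to both arms. Appendix F tells personnel to follow its procedures strictly, certification requires an exam done to protocol, and the form is to be used together with that manual, with changes to protocol written in its notes. All participants also heard the rule before baseline. This stands, and it defeats one inference a reader might draw: that follow-up blood pressure is in fact measured under different preparation by arm. What it leaves open is that no shown step turns the rule into a check at the visit.

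A reader might also infer that only controls are ever told. The documents do not support that. The telephone interview is repeated at follow-up, and its baseline version closes with the instruction, but the follow-up version is not shown. The text of the reminders promised to Living Well participants is not shown either, nor is that of the later call to those who do not schedule at month 5. Part 1 of the document was not available.

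A third inference is unequal loss to follow-up, because the month-5 contact check ("I would like to verify your contact information. Is this your correct mailing address and telephone number"?) and the promise of reminders appear only in the Living Well script. Each arm's scripts verify contact details twice, however: months 1 and 3 in General Health, months 2 and 5 in Living Well. Controls are also told to expect monthly contact and to report changed details. The timing differs; unequal loss is not shown.

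Two limits on scope also stand. Blood pressure is one of four outcomes in the Appendix F list, and nothing shown makes it primary. The shirt request adds no bias of its own, since a bare arm is required at measurement.

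**Conclusion.** The point holds as a risk. The two month-5 scripts differ by arm on preparation for an outcome measurement, and the visit form and quality checklist would not reveal a resulting imbalance. Whether one occurs depends on contacts that are not shown and on how consistently staff apply the common rule.

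The size is unknown. It is near 0 if the rule is enforced, and about 1-2 mmHg if the excess unprepared share and the pressure shift are as large as the upper assumptions in the table. The direction, against the program, rests on the further assumption that unprepared readings run high. The case for acting is not that a bias has been shown. An arm-linked difference in measurement can be removed at almost no cost now, and preparation that was never recorded cannot be reconstructed later.

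**What to change.** 1. Put the preparation and clothing paragraph from the General Health month-5 close-out into the Living Well month-5 script, in the same words, and into any follow-up reminder sent to either arm. Correct the doubled negative in its first clause when copying it.
2. Add one line to Step 1 of the In-person Data Collection Form, in both arms: caffeine, food, smoking, alcohol or heavy physical activity in the last 30 minutes, yes or no. If yes, the existing rule in Appendix F, Blood Pressure sections 2 and 3, applies. Add the same item to checklist 4.3.
3. Optional tidying: use the same contact check and the same reminder sentence in both month-5 scripts, and keep the peer-contact question as a Living Well addition.

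With the same instruction in both arms, the scripts no longer create a difference (q = 0 from this source), and the form line would show any that remained. The cost is script wording, one form line and one checklist line, and a few visits that start up to 30 minutes later. The change should be in place before the follow-up visits it is meant to protect.

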### ***Voicemail leave message 1 time only:***

Hello, my name is \_\_\_\_\_, I am calling from the University of Alabama at Birmingham about the Living Well program. At your convenience, please call us at [contact]. Thank you and have a nice day.

Hello \_\_\_\_\_, my name is \_\_\_\_\_ calling from the University of Alabama at Birmingham about the Living Well research program. How are you today?

May I please speak with \_\_\_\_\_?

- [If not speaking] Is \_\_\_\_\_ available?
- [If no] When may I call back to speak with \_\_\_\_\_? Thank you for your time.  
*[Document Date/Time to call back]* \_\_\_\_\_
- **[If yes continue when they come on the line]** Hello \_\_\_\_\_, my name is \_\_\_\_\_ calling from the University of Alabama at Birmingham about the Living Well study. How are you today?

### **I am calling today to check in with you and answer go over any questions you have about the study.**

- Have you spoken to your peer advisor? How many times since the beginning of the program have you spoken to your peer (NAME HERE).
- May I answer any questions that you may have about the study?

### **I would like to verify your contact information. Is this your correct mailing address and telephone number?**

**Yes – great thank you!** *(move to next question)*

**No – obtain correct information and update spreadsheet.**

**We also have \_\_\_\_\_ (name) as a friend or family member who would know your whereabouts in case we have trouble contacting you. Is this still the correct phone number for \_\_\_\_\_ (name)?**

**Yes – go to close out**

**No – Can you give me another person who would know your whereabouts in case we have trouble contacting you? Please think of someone who would not mind if we called them for this information.**

### ***Close out:***

- ***Thank you again for your time today.*** A member of our team will be contacting you each month by mail or phone. If you would like to reach us before we talk again you can call us at the number listed on your activity book. If your phone number or address changes, or if you have any questions about the Living Well with Diabetes study, please call us at the same number. Thank you and have a wonderful day!

## Living Well Program Participant Phone Call Script – Month 5

### ***Voicemail leave message 1 time only:***

Hello, my name is \_\_\_\_\_, I am calling from the University of Alabama at Birmingham about the Living Well program. At your convenience, please call us at [contact]. Thank you and have a nice day.

Hello \_\_\_\_\_, my name is \_\_\_\_\_ calling from the University of Alabama at Birmingham about the Living Well research program. How are you today?

May I please speak with \_\_\_\_\_?

- [If not speaking] Is \_\_\_\_\_ available?
- [If no] When may I call back to speak with \_\_\_\_\_? Thank you for your time.  
[Document Date/Time to call back] \_\_\_\_\_
- **[If yes continue when they come on the line]** Hello \_\_\_\_\_, my name is \_\_\_\_\_ calling from the University of Alabama at Birmingham about the Living Well study. How are you today?

### **I am calling today to check in with you and remind you that your 2nd study visit and telephone interview are coming up in 1 month.**

- Have you spoken to your peer advisor? How many times in the past 4 weeks have you spoken to your peer (NAME HERE)
- Your 2nd telephone interview and your study visit are coming up in 1 month. Let me tell you a little about these visits. During the telephone interview, we will ask you some questions about you and your diabetes. At the in-person data collection visit, UAB staff will do a finger stick test to check your A1c number, which is your average blood sugar level, and your blood cholesterol. They will also measure your height, weight, blood pressure, and make a list of your medications.
- Remember, you will receive a \$20 VISA gift card for completing the inperson study visit.
- Would you like to schedule this visit and telephone interview today?
  - o if no: Okay, I will give you a in 2-3 weeks.
  - o If yes, schedule date and times: Great! We will call you on the phone and send you a reminder in your mail before the visits as a reminder.
- May I answer any questions that you may have about the study?

### **I would like to verify your contact information. Is this your correct mailing address and telephone number?**

**Yes – great thank you!** *(move to next question)*

**No – obtain correct information and update spreadsheet.**

### **We also have \_\_\_\_\_ (name) as a friend or family member who would know your whereabouts in case we have trouble contacting you. Is this still the correct phone number for \_\_\_\_\_ (name)?**

**Yes – go to close out**

**No – Can you give me another person who would know your whereabouts in case we have trouble contacting you? Please think of someone who would not mind if we called them for this information.**

### ***Close out:***

- ***Thank you again for your time today.*** We will talk to you on [date/time] to complete your telephone interview and on [date/time] to complete your 2nd in person study visit. Thank you and have a wonderful day!
